3.5 Secondary Efficacy Hypotheses

We might be concerned whether the homogeneity of variance assumption for the HL method is correct. In one way this is checked by presenting both the observed ratio of the medians and the HL shift estimator. However, as a secondary supportive analysis, a direct estimation of the confidence interval of the medians is also performed using the PB method (see [Price and Bonett, 2002](#)). Here the $(1-\alpha)$ confidence interval for the ratio of medians (r) is defined as

$$r \exp\left\{\pm z_{\alpha/2} [\text{var}(\tilde{y}_1) + \text{var}(\tilde{y}_2)]^{1/2}\right\} \quad (4)$$

Where $\text{var}(\tilde{y}_j)$ is an estimate of the variances of \tilde{y}_j and $z_{\alpha/2}$ is the usual standard normal score, i.e. for a 95% confidence interval it is the value 1.96. The PB estimates of the variances are then

$$\text{var}(\tilde{y}_j) = \left\{ \frac{(y_{(n_j - c_j + 1), j} - y_{(c_j), j})}{2z_j} \right\}^2$$

With $c_j = \frac{1}{2}(n_j + 1) - \sqrt{n_j}$ rounded to the nearest integer and $z_j = \Phi^{-1}(1 - \frac{1}{2} p_j)$, and

$$p_j = \sum_{i=1}^{c_j-1} \frac{n_j!}{(n_j - i)!} (0.5)^{n_j-1}.$$

The PB CI will be calculated alongside all examples where the HL interval is calculated.

For the POX-MVA-002 example the median MLD in Group T2 (IMVAMUNE then Dryvax) is 7 and the median in Group T1 (Dryvax only) is 12, and hence the observed DAR = 0.417 with 95% PB CI of (-0.233, 0.692), the lower limit of which is negative. As noted previously, the PB method is considerably less powerful than the HL method.

Historically, the MLD has been used as a basis for measuring take attenuation. The MLA (maximum lesion AREA) is used in this trial as co-primary endpoint because it will present a more accurate measurement than using the diameter. That said, for comparison and historical purposes it is of interest to consider the MLD as a secondary supportive analysis.

The HL 95% confidence interval (and PB) will also be calculated for the DAR using the same method as defined in (4).

Secondary analyses will also be performed on separately for lesion diameter measurements and lesion area measurements on Day 6-8 and on Day 13-15.

3.6 Sample Size

The current sample size for this trial represents something close to the maximum number of subjects that can be recruited within the trial duration and should provide sufficient power for the co-primary endpoints to meet their respective objectives.

This means that the overall power for both co-primary endpoints meeting the objectives is at least 80%, i.e. should be at least 90% for each co-primary endpoint (i.e. $90\% \times 90\% > 80\%$).

Since it is required to meet both co-primary objectives, the overall sample size is fixed as the larger sample size required for each co-primary endpoint to be met with 90% power.

3.6.1 Immunogenicity Co-Primary Endpoint

The immunogenicity co-primary objective of the trial is to demonstrate the non-inferiority of MVA-BN[®] to a conventional smallpox vaccine (ACAM2000[®]) in terms of PRNT antibody response (GMTs) at the Peak Visit. Hence the following sample size calculation was performed for the co-primary immunogenicity endpoint.

Assuming a standard significance level alpha of 5%, a power of $\geq 90\%$ and the same expected individual peak PRNT GMTs in the MVA-BN[®] group (Group 1) and the ACAM2000[®] group (Group 2), then the only remaining parameter is the SD of the \log_{10} titers.

As a basis for calculation, the combined calculated value of the SD at Day 42 of the \log_{10} titers for healthy vaccinia-naïve subjects who received the standard MVA-BN[®] vaccination schedule was taken from three Phase II MVA-BN[®] studies (POX-MVA-005, POX-MVA-008 and POX-MVA-011). In total this was 419 healthy subjects and the calculated SD is 0.807 with a 95% confidence interval of (0.756, 0.866).

Adopting a worst case scenario and using the upper limit of the confidence interval, i.e. assuming $SD = 0.866$, this yields a required sample size for this trial of 175 in the PPS in both groups.

In order to account for an estimated 20% rate for exclusion from the PPS (verbal communication from USAMRIID as experience from their trials in this population), a total of 220 subjects will be recruited into each of the groups.

3.6.2 Efficacy Co-Primary Endpoint

The efficacy co-primary objective is to determine if take attenuation has occurred in Group 1 compared to Group 2 as specified in [Section 3.3.2](#).

To calculate the likely power for this analysis data from the POX-MVA-002 trial was used as a basis for calculations. Using this data a simple case resampling non-parametric bootstrap simulation was performed to estimate the likely AAR. Specifically, a random sample of size n was drawn with replacement from each group. Each individual MLD was then adjusted by a uniform random variable on the range $[-\frac{1}{2}, \frac{1}{2}]$. The MLA was imputed by assuming it is the MLD (worst case). Then, 10,000 bootstrap samples were generated. For each bootstrap sample the observed AAR was calculated. The 10th percentile of the bootstrapped lower confidence limits of the median of the differences then gives an estimate of the value of λ that can be achieved with 90% power for a given group sample size, see the [Table 5](#) below (also for 95% power and 99% power).

Table 5 Sample size calculations for the Efficacy Endpoint

n (per group) in PPS	60	75	90	105	120	150	175
Power for $\lambda=0.4$	87.0	92.8	96.3	98.0	99.1	99.8	99.9
λ that achieves 90% Power	39.1	41.0	42.2	43.0	43.7	44.8	45.3
λ that achieves 95% Power	37.2	39.2	40.6	41.7	42.5	43.8	44.4
λ that achieves 99% Power	34.3	36.1	37.4	38.9	40.1	41.8	42.7

From the above simulation results the power of passing the co-primary endpoint based on the AAR is above 90% for sample sizes of at least $n=75$ in the PPS. However, since it is known that bootstrap simulations can be somewhat optimistic and the POX-MVA-002 trial is small and has differences to those in the current POX-MVA-006 trial, it therefore seems sensible to choose a sample size at least somewhat bigger than the minimum $n=75$. Regardless, the proposed sample size of $n=175$ per group required for the immunogenicity co-primary endpoint should easily be adequate for the efficacy endpoint.

3.7 Analysis Populations

The following analysis data sets will be defined for the statistical analyses.

3.7.1 Full Analysis Set

The Full Analysis Set (FAS) consists of all subjects

- i) who had received at least one dose of trial vaccine and
- ii) for whom any post vaccination safety or immunogenicity data are available

The safety analysis and secondary supportive immunogenicity analyses will be performed on the FAS. Subjects in Group 1 who do not receive an MVA-BN[®] vaccination will not be considered enrolled in the trial (although they should receive an ACAM2000[®] vaccination outside of the protocol later).

3.7.2 Per Protocol Set

The Per Protocol Set (PPS) is the subset of subjects in the FAS who have received all vaccinations, completed all visits up until Visit 10 for Group 1 and Visit 4 for Group 2, and adhered to all protocol conditions. Subjects with only minor (not relevant) protocol deviations will be included into this dataset.

The decision whether a protocol deviation is major or minor will be made on a case-by-case basis in a data review meeting (DRM) prior to database lock.

Examples of major protocol violation are:

1. Premature discontinuation of the trial (the question “prematurely terminated the trial?” is answered with “yes” even where no other reason exists to exclude the subject from further participation in accordance with the protocol)
2. Subject did not meet all of the inclusion criteria
3. Subject met one or more of the exclusion criteria
4. Withdrawal from the second or third vaccination (Group 1)
5. Major vaccine preparation and administration deviation from specification as given in the protocol including cases where the subject fulfils at least one of the criteria specified in the protocol for withdrawal from vaccination
6. Major deviations of the visit window as determined during the DRM
7. Unallowed prior or concomitant medication
8. Missing lesion area data on Day 6-8 or Day 13-15 after ACAM2000[®] vaccination
9. Missing ELISA or PRNT titers at trial Day 0, Day 42 for subjects in Group 1 or Day 28 post ACAM2000[®] vaccination (Groups 1 and 2).

The primary endpoint dataset will be the PPS. All confirmatory testing is based on this subgroup. For further descriptive purposes, the same statistical procedures will be applied to the FAS.

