**Visit 6 (Group 1: Visit 4 + 13-15 days)**

The following tasks will be performed

- Targeted physical examination, including auscultation of heart and lungs; see [Section 8.2.3](#) for more details
- Evaluation of vital signs
- Perform ECG (if clinically indicated)
- Questions on cardiac signs and symptoms
- Review of prior/concomitant medications

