1.1 Trial Description

This is a randomized, open-label Phase III non-inferiority trial to compare indicators of efficacy for MVA-BN[®] smallpox vaccine to ACAM2000[®] in 18-42 year old healthy vaccinia-naïve subjects.

A total of 440 vaccinia-naive subjects will be assigned randomly to two parallel treatment groups in a 1:1 ratio, 220 subjects in Group 1 and 220 subjects in Group 2.

Group 1:

One 0.5 ml standard dose MVA-BN[®] liquid-frozen vaccine contains a nominal titer of 1×10^8 tissue culture infectious dose 50% (TCID₅₀) Modified Vaccinia Ankara – Bavarian Nordic (MVA-BN[®]).

Two vaccinations each of 0.5 ml MVA-BN[®] vaccine will be administered four weeks apart (Day 0 and Day 28) as a subcutaneous (s.c.) injection in the non-dominant upper arm, followed by a single vaccination of ACAM2000[®] administered four weeks after the second MVA-BN[®] vaccination (Day 56). As per the prescribing information: one dose of reconstituted ACAM2000[®] vaccine consists of $2.5\text{-}12.5 \times 10^5$ plaque forming units of live vaccinia virus. A droplet (~ 0.0025 ml) vaccine is picked up with a bifurcated needle and is administered by the percutaneous route (scarification) using 15 jabs of the bifurcated needle.

Group 2:

A single vaccination of ACAM2000[®] will be administered at Day 0.

The active phase of the trial will begin at Day 0 (Visit 1) and continue through the second MVA-BN[®] vaccination (Day 56) and until 28 days after the ACAM2000[®] vaccination of Group 1 subjects (Visit 10). The active phase of the trial will begin at Day 0 (Visit 1) and continue until 28 days after the ACAM2000[®] vaccination of Group 2 subjects (Visit 4).

A remote Follow-up (FU) Visit by telephone or email is planned six months after the last trial vaccination. Only if there is a medical need, will the subject be asked to come back to the site or at the FU Visit (and specifically in the case of deployed military subjects) at another medical unit as agreed upon by the Principle Investigator.

The total duration (including screening period) is up to 22 weeks for Group 1 and up to 18 weeks for Group 2, plus remote correspondence (e.g. a phone call or email) six months after the last vaccination. If the remote correspondence reveals a medical need or any underlying condition that requires further examinations, the subject will be called in for a physical visit.

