1.4 Endpoints

1.4.1 Co-Primary Endpoints

- PRNT GMT at the Peak Visits
- Maximum Lesion Area (MLA) in mm² after scarification with ACAM2000[®]

Both co-primary endpoint analyses will be conducted using the Per Protocol Set (PPS). However, identical secondary robustness analyses will also be conducted using the Full Analysis Set (FAS) and the Initially Seronegative Subset (ISS), a subset of the PPS.

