3.2 Immunogenicity Co-Primary Trial Hypothesis

Both co-primary trial hypotheses will be conducted on the PPS as the main analysis set. Similar analyses will also be conducted on the FAS and ISS.

The immunogenicity co-primary objective of the trial is to assess non-inferiority of MVA-BN[®] compared to ACAM2000[®] in terms of vaccinia-specific PRNT antibody response at the Peak Visits (Day 42 for Group 1 and Day 28 for Group 2).

It is assumed that the \log_{10} titers for the PRNT are normally distributed with a mean of m_1 in Group 1 and a mean of m_2 in Group 2 and a common standard deviation (SD) for both groups.

The trial should demonstrate that the Day 42 GMT of Group 1 is not lower than the Day 28 GMT of Group 2 by more than a pre-specified amount. This amount is called the non-inferiority margin (Δ).

The test of non-inferiority will be applied for the following hypothesis:

$H_0: m_1 - m_2 \leq -\Delta$ versus $H_1: m_1 - m_2 > -\Delta$, where

Δ is the non-inferiority margin and is chosen in this trial as 0.301 on the \log_{10} titers (i.e. a factor of $\frac{1}{2}$ reported on the original titer scale).

Specifically, a standard homoscedastic one sided 97.5% lower confidence limit (LCL) of the difference between the log PRNT averages of the two groups will be calculated (Group 1 – Group 2). If the LCL is above $-\Delta$ then the null hypothesis will be rejected and the non-inferiority of MVA-BN[®] to ACAM2000[®] will have been demonstrated.

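### A single Per Protocol Set for both co-primaries lets events after the Day 42 draw remove Group 1 titers from the confirmatory PRNT test; Group 2's conditions end at its own titer.

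*SAP*

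**What the plan says.** SAP 1.4.1 assigns one population to both tests: "Both co-primary endpoint analyses will be conducted using the Per Protocol Set (PPS"). SAP 3.7.2 and protocol 9.5 rest all confirmatory testing on it.

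SAP 3.7.2 builds the PPS from Full Analysis Set (FAS) subjects who "received all vaccinations, completed all visits up until Visit 10 for Group 1 and Visit 4 for Group 2" and kept to the protocol. It then lists examples of major violations:

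- item 4: withdrawal from the second or third vaccination in Group 1;
- item 8: "Missing lesion area data on Day 6-8 or Day 13-15 after" ACAM2000;
- item 9: "Missing ELISA or PRNT titers at trial Day 0, Day 42 for subjects in Group 1 or Day 28 post" ACAM2000, the last of these in either group.

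Whether a deviation is major or minor is decided case by case at a data review meeting before database lock.

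The PRNT comparison uses the Peak Visits, "Day 42 for Group 1 and Day 28 for Group 2" (SAP 3.2). In Group 1 that is Visit 6. ACAM2000 follows at Visit 7, "administered four weeks after the second MVA-BN[®] vaccination (Day 56"). Under protocol 4.2.5, a subject withdrawn after the second MVA-BN dose still attends every visit through Visit 7.

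**The concern.** A per-protocol condition should concern conduct up to the measurement being analysed. Here a Group 1 subject can receive both MVA-BN doses on schedule, give a valid Day 42 sample, and still leave the antibody comparison because of something that happened after the sample was drawn. Under protocol 4.2.5 the reasons for withholding the third vaccination include cardiac signs, adverse events and start of immune-modifying drugs. These are not plainly unrelated to immune response.

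If later loss is related to the Day 42 titer, the retained Group 1 mean moves and nothing comparable happens in Group 2. The shift enters directly into a comparison against a fixed margin of 0.301 log10. The rule also discards endpoint data that the protocol requires sites to collect.

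**Working it through.** **1. Timing of the PPS conditions** (protocol 1.5 and 4.2.2; SAP 1.1 and 3.7.2)

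| Condition | Group 1 | Group 2 |
|---|---|---|
| Peak Visit PRNT titer | Visit 6, Day 42 | Visit 4, Day 28 |
| Last vaccination | Visit 7, Day 56: 14 days after the titer | Visit 1, Day 0: before |
| Lesion areas (item 8) | Visits 8 and 9, about Days 63 and 70 (56+7, 56+14): after | Visits 2 and 3, about Days 7 and 14: before |
| Titers 28 days after ACAM2000 (item 9) | Visit 10, about Day 84 (56+28): after | Visit 4: the endpoint itself |
| Last visit required | Visit 10 | Visit 4 |

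Items 8 and 9 are worded for both groups; it is the timing that differs. Group 1's Visit 10 titers feed neither co-primary.

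**2. The reverse direction.** Item 9 applies to the lesion-area test too. A missing ELISA titer, which neither co-primary uses, removes a subject with both lesion areas. So does a missing PRNT titer. The titer due 28 days after ACAM2000 falls after both lesion areas in each group, so on this side the effect is mainly lost data and not a one-arm condition.

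**3. The plan's own figure.** Inputs from SAP 3.2 and 3.6.1: margin 0.301, SD 0.866, true difference 0, one-sided 2.5%, power 90%.

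- SE = 0.866 × √(2/175) = 0.0926; 0.301/0.0926 = 3.25.
- Noncentral-t power is 0.9001 at 175 per group and 0.8985 at 174, so 175 reproduces.
- 175/0.80 = 218.75, or 219; the plan recruits 220. At 20% exclusion, 220 × 0.80 = 176 remain per group, with power 90.2%.

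**4. Possible size of a selection effect.** The documents give neither quantity needed, so both are assumptions. Let q be the share of Group 1 subjects with a Day 42 titer who are dropped for later events, and d the amount by which their mean log10 titer lies below that of those retained. The PPS difference then shifts by q × d towards MVA-BN. With 175 per group, type I error at the margin = Φ(−1.96 + q·d/0.0926), and power at a true difference of 0 = Φ((0.301 + q·d)/0.0926 − 1.96).

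| q | d | Shift | Type I error | Power |
|---|---|---|---|---|
| any | 0 | 0 | 0.025 | 90% |
| 5% | 0.301 | 0.015 | 0.036 | 93% |
| 10% | 0.301 | 0.030 | 0.051 | 95% |
| 20% | 0.301 | 0.060 | 0.095 | 97% |
| 5% | −0.301 | −0.015 | 0.017 | 87% |
| 20% | −0.301 | −0.060 | 0.0045 | 74% |

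**5. Effect of the fix on power.** Suppose 0, 10 or 20% of the 220 Group 1 subjects are dropped only for events after Day 42. Restoring them gives 176, 198 or 220 in Group 1 against 176 in Group 2, and power of 90.2%, 91.7% or 92.9%.

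**The case against.** **One set for a joint claim is coherent.** Both co-primaries must succeed, ACAM2000 is part of Group 1's assigned regimen, and protocol 9.5 defines the PPS by adherence over each group's active phase. This makes the choice understandable. It gives no reason why a Day 42 titer should depend on a Day 70 photograph.

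**The FAS run covers it.** SAP 1.4.1 calls for identical robustness analyses on the FAS, SAP 3.8.1 uses available cases, and SAP 5.1 lists a FAS non-inferiority table. Subjects dropped after Day 42 are in it, so a marked effect would probably show. This stands as mitigation. But SAP 3.7.2 labels the FAS run descriptive, and the confirmatory result does not depend on it.

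**The list is only of examples.** True, and the meeting may judge some lapses minor. Receiving all vaccinations and completing all visits are, however, in the definition itself. Assay staff and the take review committee are blinded (protocol 7.1 and 7.5), but neither document says that the data review meeting is masked to titers and lesion areas.

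**Group 2 may also be affected after its titer.** Item 1, premature discontinuation, has no stated time limit, so a literal reading could catch a Group 2 subject who stops after Visit 4. Protocol 9.5 limits the PPS to the active phase, which ends at Visit 4 in Group 2. This is at most a minor exception.

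**Stronger readings a reader might infer.** One is that the PRNT test is underpowered. If the planned 20% accrued evenly over Group 1's ten visits, with the same per-visit loss in Group 2, retention would be 0.8^(1/10) = 0.978 per visit. That leaves 176 in Group 1 and 201 in Group 2, with power 91.9%. A shortfall needs something like 30% exclusion in Group 1 (154 subjects): 89.9% against 201 or 88.1% against 176. No document gives such a rate. At the observed SD of 0.807 those figures are 93.5% and 92.1%. Another is that deployment drives the loss; it is not among the withdrawal criteria in protocol 4.2.5.

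**Conclusion.** The point holds as a risk of selection. The confirmatory PRNT test conditions Group 1, and in practice only Group 1, on events after its endpoint was measured, and endpoint titers collected under the protocol are set aside. The lesion-area test in turn loses subjects for titers it does not use.

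A reader might conclude that the randomised comparison is broken or that the result will favour MVA-BN. The documents do not support that: they do not say how many Group 1 subjects would be lost after Day 42 or whether their titers would differ. With no titer difference there is no distortion. With lower titers among those dropped, the test becomes too liberal; with higher titers, it loses power. The figures in the working show what could follow under assumed values and are not estimates.

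Planned power is adequate at 20% exclusion. The change is a cheap improvement that removes an avoidable dependency. It does not correct a demonstrated error in the sample size or the test.

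**What to change.** In protocol 9.5 and SAP 3.7.2, replace the single PPS with two sets:

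- **Immunogenicity PPS:** eligible; vaccinations due before the Peak Visit received; baseline and Peak Visit PRNT titers present; no major deviation up to the Peak Visit.
- **Efficacy PPS:** all vaccinations received; both lesion areas present; no major deviation up to Day 13-15 after scarification; no titer requirement.

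SAP 3.7.3 makes the Initially Seronegative Subset part of the PPS, so state that for each endpoint it is the subset of the matching PPS with seronegative baseline ELISA and PRNT.

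Hold the data review meeting masked to titers and lesion areas. Report how many Group 1 subjects with a Day 42 titer were lost after it, with reasons.

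The cost is amended wording in both documents, additional population flags, and table titles that name their parent set. The two co-primaries will have slightly different denominators. No planned power is lost, because Group 1's number in the PRNT test can only stay the same or rise. The new immunogenicity set still spans 42 days and two doses in Group 1 against 28 days and one dose in Group 2; that difference comes from the design and remains.

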3.7.3 Initially Seronegative Subset

As seen in supposedly vaccinia-naive populations in previous MVA-BN[®] trials, some subjects will most likely be initially tested seropositive at Visit 1 prior to vaccination in either the ELISA or PRNT. An additional subgroup analysis based on the subset of the PPS of initially seronegative subjects, the Initially Seronegative Subset (ISS) will therefore be performed which will provide assurances that the results have not been affected by the possible inclusion of some vaccinia-experienced subjects. In doing so it should be noted that some of the initially seropositive values might be false positive values. However, there is no reliable way to determine which seropositive cases are false positive and which are true positive values, and the ISS is therefore a conservative approach to validating the results in a confirmed naïve population.

A subject of the PPS will be part of the ISS, if the subject is seronegative for both ELISA and PRNT at baseline.

The ISS population will be used as an additional robustness analysis set for the immunogenicity and the demographic analyses.

3.8 Definitions, Data Conventions and Handling of Missing Data

3.8.1 Missing Data

Analysis of immunogenicity variables will be done on a valid case basis, i.e. for missing observations no imputation technique such as “Last observation carried forward” (LOCF) will be applied, since this could introduce an optimistic bias into the analysis.

For the analysis of safety data incomplete AE and medication start and end dates will be imputed in order to assign these events to the correct vaccination period (see [Section 3.8.2](#)).

Missing Vital Signs data for Visit 1 will be imputed using screening (or latest re-screening) values. However, this will be displayed as ‘Baseline’ values in the tables and listing for Vital Signs data without reference to whether the data originated from Visit 1 or SCR.

All data will be listed and summarized as captured in the eCRF. However, it may be necessary to impute incomplete AE and medication start and end dates in order to assign these events to the correct vaccination period, which will be done as follows:

For prior and concomitant medication and AEs imputation of partial start and end dates will be done for analysis purpose according to the following rules:

Missing	Rule for start date	Rule for end date	Flag for imputation
Day	First of month*	Last of month*	D
Month [†]	1. January*	31. December*	M
Year [†]	no imputation	Last visit date	Y

* Unless the imputed start date is before first visit date, in which case first visit date is used; or the imputed stop date is after last visit date in which case last visit date available is used.

† It is assumed that a missing month implies a missing day as well, and that a missing year implies a missing month and day.

All listings will display the original dates as captured in the eCRF.

For analysis of efficacy data if one or both of the Day 6-8 or Day 13-15 photographs are missing then the photograph will be recorded as missing and the assessment of attenuation will not be made.

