3.8.2 Assignment of AEs to Vaccination Period

Each AE will be assigned to a vaccination period using date and time of vaccination and date and time of start of AE. If not specified otherwise all AE tables will be presented divided into the following vaccination periods:

For Group 1:

- Vaccination Period 1 covers from Visit 1 (immediately after the first vaccination) until Visit 4 (just before the second vaccination).
- Vaccination Period 2 covers from Visit 4 (immediately after the second vaccination) until Visit 7 (just before the third vaccination).
- Vaccination Period 3 covers from Visit 7 (immediately after the third vaccination) until Visit 10.
- The Overall MVA-BN[®] Vaccination Period is the combination of Vaccination Periods 1 and 2.

For Group 2:

- Vaccination Period 1 covers from Visit 1 (immediately after the first vaccination) until Visit 4.

If start time is missing and start date of AE coincides with the date of a vaccination, the AE will be assigned to the vaccination period corresponding to the vaccination on this date.

Each AE starting at or after first vaccination not matching the definition of a solicited AE is defined as an unsolicited AE. If a solicited AE begins outside of the 15-day window following the last vaccination it will be considered an unsolicited AE regardless of the preferred term. If start time is missing and start date coincides with date of current vaccination, it will be regarded as a treatment emergent AE. If the start date is (partially) missing the AE will be regarded as a treatment emergent AE following the worst case principle. If the AE cannot be assigned to a vaccination period 1 or 2 because of a (partially) missing start date it will be assigned to the overall MVA-BN[®] vaccination period (Group 1). If the AE cannot be assigned to vaccination period 2 or 3 then it will not be assigned to a vaccination period. AEs which cannot be assigned

to a vaccination period will still be included in per subject based tables and in the listings (with partial dates).

AEs with onset after the active trial phase will be considered to fall within the FU phase.

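### SAP 3.8.1 can date an AE with a partial start date before the vaccination it followed, moving Group 1 ACAM2000 events into an MVA-BN period, and the SAP does not say whether 3.8.1 or 3.8.2 decides the period

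*SAP*

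**What the plan says.** SAP 3.8.1 (Missing Data) gives the purpose: "incomplete AE and medication start and end dates will be imputed in order to assign these events to the correct vaccination period", with a pointer to 3.8.2. The table of rules is then introduced with the statement that "imputation of partial start and end dates will be done for analysis purpose according to the following rules". When only the day of a start date is missing, the table entry is "First of month". With the month missing it is 1 January, and with the year missing nothing is imputed. The footnote sets the only floor: "Unless the imputed start date is before first visit date, in which case first visit date is used". That date is not defined. The schedule tables in SAP Section 2 place a Screening visit up to 70 days before Visit 1, so either visit could be meant.

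SAP 3.8.2 assigns each AE to a period by comparing its start with the vaccination dates. For Group 1, Periods 1 and 2 follow the two MVA-BN doses and Period 3 follows ACAM2000. Group 2 has one period. The same section adds three rules for incomplete dates:

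- On treatment-emergent status: "If the start date is (partially) missing the AE will be regarded as a treatment emergent AE following the worst case principle".
- A fallback for Periods 1 and 2, which sends the AE to the combined MVA-BN period, begins: "If the AE cannot be assigned to a vaccination period 1 or 2 because of a (partially) missing start date it will be assigned".
- On Periods 2 and 3: "If the AE cannot be assigned to vaccination period 2 or 3 then it will not be assigned to a vaccination period". Such AEs stay in the per-subject tables and the listings.

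SAP 3.8.3 uses imputed dates for the duration of unsolicited AEs but does not calculate their relative onset day when the start date is partial.

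**The concern.** An imputation meant to find the right vaccination period should use the vaccination dates. This one does not. An AE that begins after a vaccination, in the same calendar month, is pulled back to the first of that month and so usually to before the dose. The first visit floor cannot prevent this for the second and third vaccinations, because it lies weeks earlier on any reading.

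The safety objective (Protocol 3.2, SAP 1.2.2) compares MVA-BN, ACAM2000 alone and ACAM2000 after MVA-BN. By default the AE tables are split by vaccination period, and SAP 5.1 includes a per-period table of cardiac AESI follow-up. A Period 3 event moved to Period 2 is charged to the investigational vaccine instead of the comparator. It also leaves the period that is set against Group 2's only period. If the first visit is Visit 1, Group 2 loses no events this way, so ACAM2000 after priming would look slightly better tolerated for a reason that lies in the date rule alone.

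The second problem is precedence. Once 3.8.1 has filled in a day or month, the date is complete and a period can always be found. The 3.8.2 fallbacks would then apply only when the year is missing, although their wording covers partially missing dates in general. Two programmers could each follow the SAP and produce different period tables.

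**Working it through.** The plan gives no figure on this point to reproduce, so the rule was applied directly.

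**Inputs from the documents.** Vaccinations on Days 0, 28 and 56 in Group 1 and Day 0 in Group 2 (SAP 1.1). Imputed start = the later of the first of the onset month and the first visit date (SAP 3.8.1). Periods as in SAP 3.8.2.

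**Assumptions.** Only the day is missing. Vaccination dates are spread evenly over a four-year calendar (1,461 days, 48 months). Onset is uniform over days 0-27 after the vaccination, with days 0-13 and 14-27 as the range.

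**Formula.** Take an onset *l* days after a vaccination. The first of the onset month precedes that vaccination exactly when the onset falls in the same month and the vaccination was not on the 1st. In a month of *m* days, *m* − *l* − 1 vaccination days meet this. Summed over the calendar:

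share(*l*) = [1461 − 48(*l* + 1)] / 1461

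This is linear in *l*, so a uniform range needs only its mean lag:

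| Assumed onset | Mean *l* | Calculation | Dated before own vaccination |
|---|---|---|---|
| Days 0-27 | 13.5 | (1461 − 696)/1461 | 52% |
| Days 0-13 | 6.5 | (1461 − 360)/1461 | 75% |
| Days 14-27 | 20.5 | (1461 − 1032)/1461 | 29% |
| Day 10 only | 10 | (1461 − 528)/1461 | 64% |

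A day-by-day run through the calendar gives the same values (0.524, 0.754, 0.294, 0.639).

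**Effect of the floor.**

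- *First visit = Screening.* The shares hold for every period in both groups. Screening lead times from 1 to 70 days give the same result, because any Screening date is before Day 0.
- *First visit = Visit 1.* The share is 0% for the first vaccination (Group 1 Period 1 and all of Group 2). The floor then equals the vaccination date, and 3.8.2 counts an onset on that date, with time missing, in that vaccination's period. For Group 1 Periods 2 and 3 the shares are unchanged.

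**Where Period 3 events go** (onset over days 0-27): 52.1% to Period 2, 0.2% to Period 1, and 47.6% stay.

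**Example.** Vaccinations on 10 March, 7 April and 5 May. An AE that truly starts on 15 May but is recorded only as May is imputed to 1 May. That lies between the second and third vaccinations, so an ACAM2000 event is tabulated in MVA-BN Period 2 under both readings of first visit.

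**Month missing.** If all of a subject's visits fall in one calendar year, 1 January precedes the first visit and the start becomes the first visit date. Every Period 2 or 3 AE with a missing month would then leave its period.

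**The case against.** The best defence is that the two sections can be read together. On one reading, the AE-specific text in 3.8.2 decides the period and the imputed dates serve medications and AE duration; then no AE moves. On the other, 3.8.1 handles a missing day or month and the 3.8.2 fallbacks handle a missing year. Both are workable, so the rules are not irreconcilable. But the SAP does not choose, and 3.8.1 states period assignment as its purpose, which favours the reading under which AEs move.

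A reader might infer three stronger things that the documents do not support:

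- *That the worst-case sentence in 3.8.2 contradicts 3.8.1.* It concerns treatment-emergent status, not period. It keeps these AEs treatment emergent and so limits the harm. The tension is with the fallback sentences.
- *That Group 2 AEs become pre-vaccination signs.* This needs the first visit to be Screening and the worst-case sentence to be ignored. Protocol 8.1.2 and 8.1.3 also record pre-vaccination events in a separate CRF section. A residual risk remains on the Screening reading: SAP 3.10.4 defines baseline signs by start date, and the SAP definition of a causally related AE does not presume relatedness when the relationship is missing and onset precedes the first vaccination.
- *That the period-level counts are wrong.* The percentages are shares of AEs with a missing start day, not of all AEs. Solicited symptoms are recorded daily, most active-phase visits are one or two weeks apart and queries are settled before lock, so partial dates are probably few.

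It is also fair to say that a shift from Period 2 to Period 1 stays within the overall MVA-BN period. The shift that changes the vaccine attribution is from Period 3 to an MVA-BN period.

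**Conclusion.** The concern holds in limited form. If 3.8.1 governs, about half of AEs with a missing start day (52%; 29-75% across the assumed onset ranges) are dated before the vaccination they followed. Group 1 ACAM2000 events can then be counted under MVA-BN on either reading of first visit. For the first vaccination, and hence Group 2, the error arises only on the Screening reading. Separately, the SAP does not say whether the imputed date or the fallbacks decide the period when only the day or month is missing.

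These shares rest on evenly spread vaccination dates and assumed onset distributions. The effect on total counts cannot be computed, because the documents give no frequency of partial dates. Treatment-emergent status under 3.8.2, per-subject totals and both co-primary endpoints are untouched. The change is worth making because it is cheap and because a single misattributed cardiac event would matter in a per-period AESI table.

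**What to change.** In SAP 3.8.1, for AEs with a missing start day or month, set the imputed start to the later of:

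- (a) the first of the recorded month or year; and
- (b) the date of the most recent vaccination given before the AE was first recorded. For an AE recorded as immediate after vaccination at a visit, use that visit's vaccination.

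Make an exception where the end date or other recorded data show an earlier onset. The recorded month or year is itself such data, so a vaccination given after it ended cannot serve as the floor. In the example above, the start becomes 5 May and the AE stays in Period 3.

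State that this imputed date decides the vaccination period, and define the first visit date. Keep the worst-case treatment-emergent sentence in 3.8.2. Keep the fallbacks too, but limit them to AEs whose period still cannot be determined, such as those with a missing year; they are the only period-assignment rule for that case. Keep the imputation flag.

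The cost is one paragraph of SAP text and minor programming before database lock, when a final SAP version is due in any case.
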